4.5.3 Special Diet or Activities

Patients taking ubrogepant must refrain from consuming grapefruit or grapefruit juice from the time the consent form is signed until completion of the study. In addition, patients will be asked to refrain from sleeping and from consuming caffeine for at least 2 hours after they take IP.

Alcohol intake should be limited to no more than 3 drinks per day throughout the study. A drink is defined as a 12-ounce can/bottle of beer, a 4-ounce glass of wine, or 1 ounce of liquor.

5. Study Treatments

5.1 Study Treatments and Formulations

Ubrogepant [REDACTED] oral compressed tablets containing 50 mg of ubrogepant.

Ubrogepant placebo [REDACTED] tablets.

5.2 Control Treatment

This study does not include a control treatment.

5.3 Methods for Masking/Blinding

Ubrogepant will be provided to patients in the ubrogepant arms. A modified double-dummy design will be used to maintain the study blind for the ubrogepant arms. Patients randomized

to the ubrogepant arms will be provided IP in identical blister cards to maintain the blinding, and instructed to take 2 tablets to treat their migraine attack regardless of the dose group to which they are assigned. The patients randomized to the usual-care arm will not be dispensed ubrogepant.

5.4 Treatment Allocation Ratio [REDACTED]

Patients will be randomized (1:1:1) to 1 of the following 3 treatment groups: usual-care, ubrogepant 50 mg, or ubrogepant 100 mg. The study is open-label; however, randomization to the ubrogepant arms (50 and 100 mg) will be blinded. If and when an interim analysis occurs, the doses will be unblinded (see Section 7.6).

[REDACTED]

[REDACTED]

[REDACTED]

5.5 Method for Assignment to Treatment Groups/Randomization

Prior to initiation of study treatment, each patient who provides informed consent will be assigned a patient number that will serve as the patient identification number on all study documents.

At the time of randomization (ie, Visit 2), eligible patients will be randomly assigned to 1 of 3 treatment arms in a 1:1:1 ratio to receive usual-care, ubrogepant 50 mg, or ubrogepant 100 mg or [REDACTED].

[REDACTED]

An automated interactive web response system (IWRS) will be used to manage the randomization and treatment assignment. Allergan Biostatistics (randomization programmer) will prepare the randomization codes.

Investigational product will be labeled with medication kit numbers. The IWRS will provide the site with the specific medication kit number(s) for each randomized patient in the ubrogepant arms at the time of randomization. Sites will dispense IP according to the IWRS instructions. Sites will receive the IWRS confirmation notifications for each transaction. All notifications will be maintained with the study source documents.

5.6 Treatment Regimen and Dosing

5.6.1 Ubrogепant

Table 2 presents the treatments that will be administered in this study. Patients randomized to the ubrogепant arms will be instructed to take 2 tablets to treat their migraine attack regardless of the dose group to which they are assigned.

Table 2 Treatments Administered for Initial and Optional Second Dose

Drug/Dose	Dose Frequency	Route of Administration	Investigational Product Administered	
			Initial Dose	Optional Second Dose
Ubrogепant 50 mg	Up to 8 times/4 weeks for 1 year (with optional second dose – maximum 16 times/4 weeks)	Oral (tablet)	Ubrogепant 50 mg/ placebo 50 mg	Ubrogепant 50 mg/ placebo 50 mg
Ubrogепant 100 mg	Up to 8 times/4 weeks for 1 year (with optional second dose – maximum 16 times/4 weeks)	Oral (tablet)	Ubrogепant 50 mg/ ubrogепant 50 mg	Ubrogепant 50 mg/ ubrogепant 50 mg

Patients randomized to the ubrogепant arms will be allowed to treat up to 8 qualifying migraine headaches (of any pain severity) per 4-week period throughout the course of a year. Patients will be instructed to treat the migraine headaches as soon as possible when all of the following conditions are met:

- At least 48 hours since the last dose of ubrogепant
- At least 48 hours of pain freedom (ie, no headache for at least 48 hours)
- The migraine headache started less than 4 hours ago
- The migraine headache is not already resolving on its own
- Prohibited medication has not been taken

5.6.2 Usual Care

Patients randomized to the usual-care arm will be instructed to treat their migraine with the medication(s) that they routinely take to relieve a migraine attack. Their usual medication(s) for acute treatment will be identified at Visit 1. At any time during the study, the patient's treating physician or the investigator may instruct these patients to change their migraine treatment. Any changes to the usual medication(s) identified at Visit 1 will be recorded in the

eCRF. There will be no limitations to the number of migraines treated and no qualifiers to treat a migraine for patients in this arm.

5.6.3 Optional Second Dose and Rescue Medication

Patients who took ubrogepant for their initial dose will have the opportunity to take an optional second dose of ubrogepant if they continue to have headache of any pain severity or if headache (of any pain severity) returns. An optional second dose can be taken from 2 to 48 hours after the initial ubrogepant dose.

[REDACTED]

[REDACTED]

[REDACTED]

5.7 Storage of Investigational Products/Treatments

Investigational product at the site must be stored at room temperature in a securely locked cabinet. Further details regarding the storage of the IP are in the Study Reference Manual.

6. Response Measures and Summary of Data Collection Methods

[REDACTED]

[Redacted]

[Redacted]

[Redacted]

[Redacted]

- [Redacted]

- [Redacted]

- [Redacted]

- [Redacted]

[Redacted]

[Redacted]

[Redacted]

[Redacted]

- [Redacted]

- [Redacted]

- [Redacted]

- [Redacted]

[Redacted]

[Redacted]

[Redacted]

[Redacted]

[Redacted]

[Redacted]

[Redacted]

[Redacted]

6.2.2 Events of Clinical Interest

Selected nonserious and serious events are of clinical interest and will require immediate reporting, recording and follow-up. The following events will be closely monitored:

- Suicidal ideations with intent, with or without a plan, (ie, Type 4 or 5 on the C-SSRS) or any suicidal behaviors
- Elevated ALT or AST laboratory value that is ≥ 3 times the ULN
- Potential Hy's law cases: elevated ALT or AST laboratory value that is ≥ 3 times the ULN and an elevated total bilirubin laboratory value that is ≥ 2 times the ULN and, at the same time, an alkaline phosphatase laboratory value that is < 2 times the ULN.

Reporting requirements for ALT or AST elevations and potential Hy's law cases are outlined in Sections 9.5 and 9.6. Responses to the C-SSRS that meet the above criterion will be captured in the electronic tablet (eTablet) and monitored by Allergan. Events that are determined to be AEs or SAEs must be reported appropriately via the designated eCRF pages and forms.

6.2.3 Clinical Laboratory Determinations

Blood and urine samples for clinical laboratory tests will be collected at the visits outlined in Table 1. Hematology, chemistry, and urinalysis will be conducted at these visits. The investigator will assess the clinical significance of any values outside the reference ranges provided by the central laboratory. A central laboratory will be used to evaluate all urine and blood samples, which will be collected, processed, and stored according to the instructions provided by the laboratory. Patients with abnormalities judged to be clinically significant at Screening (Visit 1) will be excluded from the study. WOCBP will be required to have a urine pregnancy test at all visits. A positive pregnancy test at Visit 1 or Visit 2 will exclude the patient from participation in the study. Investigators may also perform unscheduled clinical laboratory determinations at any time for the purpose of patient safety. Patients are not required to fast overnight before coming in for their appointments.

The clinical laboratory parameters to be measured are shown in Table 3.

Table 3 Clinical Laboratory Parameters

Category	Parameter
Chemistry	Sodium, potassium, chloride, bicarbonate, glucose, blood urea nitrogen, creatinine, total bilirubin, alkaline phosphatase, aspartate aminotransferase, alanine aminotransferase, lactate dehydrogenase, creatine kinase, total protein, albumin, calcium, phosphorus, uric acid, total cholesterol, high density lipoprotein, low density lipoprotein, total triglycerides; the estimated glomerular filtration rate will be calculated by the central laboratory
Hematology	Hemoglobin; hematocrit; red blood cell count; red blood cell indices (mean corpuscular volume, mean corpuscular hemoglobin, mean corpuscular hemoglobin concentration); white blood cell count, including differential (neutrophils, lymphocytes, monocytes, eosinophils, and basophils); platelet count
Urinalysis	Urine dipstick for specific gravity, pH, protein, glucose, ketones, bilirubin, and blood; microscopic examination including red blood cells/high-power field, white blood cells/high-power field, and casts/low-power field

6.2.4 Vital Sign Measurements

Vital sign measurements, including sitting and standing BP, sitting and standing pulse rate, respiratory rate, temperature, and body weight will be taken, according to [Table 1](#). Sitting and standing BP and pulse rate will be determined as follows: BP and pulse measurements will be performed after the patient sits quietly for 5 minutes, followed by a second set of measurements taken after the patient stands for 3 minutes (but no longer than 10 minutes).

6.2.5 Physical Examinations

A complete physical examination will be performed at the visits outlined in [Table 1](#). A professionally trained physician or healthcare professional licensed to perform physical examinations will examine the patient for any detectable abnormalities of the following body systems: general appearance; neck (including thyroid); head, eyes, ears, nose, and throat; lungs; heart/cardiovascular; abdomen; neurologic; extremities; back; musculoskeletal; lymphatic; skin; and other. The neurologic examination should be conducted to detect the presence of any significant sensory/motor abnormalities.

6.2.6 Electrocardiograms

A 12-lead ECG will be performed at the visits outlined in [Table 1](#). ECGs will be sent to a central ECG laboratory to be centrally read by a cardiologist. All ECGs should be performed after the patient has been supine for at least 5 minutes. A copy of the ECG will be saved as a source document. ECGs will be transmitted electronically to the central ECG laboratory for analysis according to the instructions provided by the laboratory. The overall interpretation

of the clinical significance of the ECG will be determined by the investigator and recorded in the patient's eCRF in the source notes.

6.2.7 Suicidality Assessment

The C-SSRS is a clinician-rated instrument that reports the severity of both suicidal ideation and behavior. Suicidal ideation is classified on a 5-item scale: Type 1 (wish to be dead), Type 2 (nonspecific active suicidal thoughts), Type 3 (active suicidal ideation with any methods [not plan] without intent to act), Type 4 (active suicidal ideation with some intent to act, without specific plan), and Type 5 (active suicidal ideation with specific plan and intent). The C-SSRS also captures information about the intensity of ideation, specifically the frequency, duration, controllability, deterrents, and reasons for the most severe types of ideation. Suicidal behavior is classified on a 5-item scale: Type 0 (no suicidal behavior), Type 1 (preparatory acts or behavior), Type 2 (aborted attempt), Type 3 (interrupted attempt), and Type 4 (actual attempt). More than 1 classification can be selected provided they represent separate episodes. For actual attempts only, the actual or potential lethality is classified for the initial, most lethal, and most recent attempts. The C-SSRS will be completed at all study visits. At all visits, the C-SSRS will be completed for ideation and behavior since the previous visit. The C-SSRS will be completed on the eTablet by the investigator or designee with current and valid training in administering the assessment. A patient should not be released from the study center until the results of C-SSRS are reviewed and it is confirmed that the patient is not considered to be at risk.

6.2.8 Cardiovascular Disease Risk

Patients will be classified to 1 of 3 coronary heart disease risk categories (low, moderate, high) based on the National Cholesterol Education Program (NCEP; [NIH Publication No. 01-3670, 2001](#)).

- Category 1 (High Risk): > 20% 10-year cardiovascular (CV) risk
- Category 2 (Moderate Risk): 10 to 20% 10-year CV risk
- Category 3 (Low Risk): < 10% 10-year CV risk

Risk of cardiovascular disease will be assessed in the lead-in studies using an algorithm based on NCEP and the Framingham risk factors, along with the presence of cardiovascular heart disease or other clinical forms of atherosclerotic disease, as well as diabetes.

6.3 Other Study Supplies

The following will be provided by Allergan:

- All supplies needed for blood and urine sampling (central laboratory analysis, urine culture/sensitivity), urine dipstick reagent strips, and urine pregnancy tests
- Shipping materials for shipment of laboratory samples to central laboratory
- All supplies needed for ECG assessment, including ECG machine
- eDiary
- eTablet

6.4 Summary of Methods of Data Collection

An IWRS will be used to randomize patients and manage ubrogepant inventory. Data for this study will be collected using eCRFs via an electronic data capture system. Source documents will be used at the sites and may include a patient's medical record, hospital charts, clinic charts, the investigator's patient study files, as well as the results of diagnostic tests, such as laboratory tests, ECGs, etc. Centralized vendors will be used for the analysis of all blood/urine samples and ECG assessments. Additional information on the collection and handling of samples is detailed in respective laboratory manuals.

Patients in the ubrogepant arms will use an eDiary to record details associated with their migraine attack, [REDACTED]

[REDACTED]. Patients in the usual-care arm will use the eDiary to record details associated with their migraine attack before it is treated with their usual medication.

The C-SSRS will be conducted as a clinical interview at each visit and recorded by a qualified site staff member via an eTablet.

7. Statistical Procedures

7.1 Analysis Populations

7.1.1 Modified Intent-to-Treat Population

The Modified Intent-to-Treat (mITT) population will consist of all randomized patients who received at least 1 dose of IP (ubrogepant) and had at least 1 post-treatment efficacy

assessment in this study. The mITT population is only defined for the ubrogepant arms, as no efficacy measurements will be collected from patients in the usual-care arm.

7.1.2 Safety Population

The Safety population will be defined separately for the ubrogepant arms and the usual-care arm.

- Ubrogepant arms: All randomized patients who received ≥ 1 dose of treatment
- Usual-care arm: All randomized patients in the usual-care arm.

The purpose of the usual-care arm is to contextualize any safety findings that may occur in the ubrogepant treated patients over the course of 12 months. As such, data from all patients randomized to the usual-care arm, regardless of whether the patient used medication to treat migraine, will be included in the safety analyses.

[REDACTED]

[REDACTED]

[REDACTED]

[REDACTED]

[REDACTED]

[REDACTED]

[REDACTED]

[REDACTED]

[REDACTED]

[REDACTED]

[REDACTED]

- | [REDACTED]
- | [REDACTED]
- | [REDACTED]
- | [REDACTED]
- | [REDACTED]
- | [REDACTED]
- | [REDACTED]
- | [REDACTED]
- | [REDACTED]
- | [REDACTED]
- | [REDACTED]
- | [REDACTED]

[REDACTED]
[REDACTED]
[REDACTED]

7.3 Hypothesis and Methods of Analysis

[REDACTED] [REDACTED]
[REDACTED]
[REDACTED]
[REDACTED]
[REDACTED]
[REDACTED]

[Redacted text block]

[Redacted text block]

[Redacted text block]

[Redacted text block]

- [Redacted list item]

- [Redacted list item]

[Redacted text block]

7.3.2 Safety Analyses

The safety analyses will be performed using the Safety population. The safety parameters will include AEs, clinical laboratory evaluations, vital sign measurements, ECG parameters,

and the C-SSRS. For each of the clinical, laboratory, vital sign, and ECG parameters, the last nonmissing safety assessment before the first dose in the lead-in study will be used as the baseline for all analyses of that safety parameter. Continuous variables will be summarized by the number of patients and mean, SD, median, minimum, and maximum values. Categorical variables will be summarized by number and percentage of patients.

7.3.2.1 Adverse Events

AEs will be coded by system organ class and preferred term using the Medical Dictionary for Regulatory Activities.

An AE will be considered a treatment-emergent adverse event (TEAE) if it was present after the first dose of treatment in the lead-in study or was present before the date of the first dose of treatment in the lead-in study and increased in severity after the first dose of treatment in the lead-in study. If more than 1 AE was reported before the first dose of treatment of the lead-in study and coded to the same preferred term, the AE with the greatest severity will be used for comparison with the AEs occurring after the first dose of treatment of the lead-in study. An AE that occurs after Visit 16 for patients with Visit 16, or more than 30 days after the last visit or last treatment, whichever is later, for patients without Visit 16 will not be considered as a TEAE.

The number and percentage of patients reporting TEAEs after randomization in each treatment group will be tabulated by descending percentage in the highest dose group, by system organ class and preferred term, and further categorized by severity and causal relationship to the study treatment. If more than 1 AE is coded to the same patient, the patient will be counted only once for that preferred term using the greatest severity and strictest causality for the summarization by severity and causal relationship.

The incidence of common ($\geq 2\%$ of patients in any treatment group) TEAEs will be summarized by system organ class, preferred term, and treatment group.

The total number of TEAEs by severity and causal relationship to the study treatment will be summarized by treatment group.

A SAE that occurred between the date of the first dose of treatment in the lead-in study and Visit 16 for patients with Visit 16, or within 30 days after the last visit or last treatment, whichever is later, for patients without Visit 16, inclusive, will be considered an on-therapy SAE. The number and percentage of patients who have on-therapy SAEs after randomization will be summarized by preferred term and treatment group.

The number and percentage of patients who had AEs leading to premature discontinuation of the study treatment will be summarized by preferred term and treatment.

For all screened patients, separate tabular displays will be presented for patients who died, patients with SAEs, and patients with AEs leading to premature discontinuation.

The number and percentage of patients with TEAEs of clinical interest will be summarized by preferred term and treatment group. TEAEs of clinical interest include triptan-associated TEAEs, abuse-related TEAEs, hepatic injury TEAEs, cardiac arrhythmias TEAEs, central nervous system TEAEs, vascular disorders TEAEs, embolic and thrombotic events TEAEs, hypertension TEAEs, ischemic heart disease TEAEs, and suicide/self-injury TEAEs.

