5.1.1.1.3 Statistical Methodology

The methodologies defined below apply as specified to individual endpoints defined in this SAP. All statistical tests will be 2-sided hypothesis tests performed at the 5% level of significance for main effects. All confidence intervals will be 2-sided 95% confidence intervals, unless stated otherwise.

Table 5-2 Statistical Methodology

Methodology	Description
M1 Categorical counts	
 • Number of participants in individual categories 
 ○ Participants with ≥ 1 qualifying event counted once per individual category
M2 Categorical descriptives	
 • Number and percentage of participants in individual categories 
 ○ Participants with ≥ 1 qualifying event counted once per individual category • N1 if proportion denominator \neq number of participants in the population (standard percentage denominator) 
 ○ N1 = participants with non-missing baseline value
M3 PCS descriptives	
 • Number and percentage of participants meeting potentially clinically significant (PCS) criteria 
 ○ Participants with ≥ 1 qualifying event counted once per PCS category • Percentage denominator = number of participants with all non-missing non-PCS baseline and ≥ 1 non-missing postbaseline assessment 
 ○ Unevaluable assessments considered missing
M4 Shift analysis	
 • Number and percentage of participants in individual baseline and postbaseline categories • Percentage denominator = number of participants in individual baseline categories • N1 = participants with non-missing values at both baseline and the specified postbaseline analysis visit
M5 Continuous descriptives	
 • N1, mean, standard deviation (SD), median, minimum, maximum • N1 = participants with non-missing value
M6 CFB descriptives	
 • Continuous descriptives for baseline, postbaseline, and change from baseline (CFB) values • N1 = participants with non-missing values at both baseline and the specified postbaseline analysis visit

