5.1.1.4.2 Adverse Events

The following adverse event (AE) terms are defined:

Table 5-19 AE Terms

Term	Description
Treatment-emergent	An event that initially occurs or increases in intensity on or after the initial dose of treatment of the lead-in study. An event that occurs after Visit 16 for participants with Visit 16, or more than 30 days after the last visit or last treatment, whichever is later, for participants without Visit 16 will not be considered as treatment-emergent.

Term	Description
On-therapy	An event where: 
 • Treatment start date of the lead-in study \leq event start date \leq Visit 16 for participants with Visit 16, or within 30 days after the last visit or last treatment, whichever is later, for participants without Visit 16

AEs, encompassing abnormalities and surgeries reported as occurring after the Screening Visit, will be coded using MedDRA version 20.1 or newer. Unique participants reporting AEs in the following AE categories will be summarized by treatment group for the Safety Population as follows:

Table 5-20 AE Summaries

Parameter	Description	Timing	Methodology
Overall summary	Overall summary only for the following categories: 
 • Treatment-emergent AEs (TEAEs) • Treatment-related TEAEs • On-therapy serious adverse events (SAEs) • Deaths • AEs leading to discontinuation Subgroup analyses by Cardiovascular Risk Category and by renal function class	From randomization date to Visit 16 for participants with Visit 16, or within 30 days after last visit or last treatment, whichever is later, for participants without Visit 16	Categorical descriptives

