TEAEs	Summary by 
 • SOC and PT for all participants and by subgroup analyses: 
 ○ by Sex ○ by Age Group <40 vs \geq40 ○ by Age Group <65 vs \geq65 ○ by Race White vs All other races ○ by cardiovascular risk category ○ by renal function class • SOC and PT for concomitant medication classes used by at least 10% of participants in at least one treatment group • SOC, PT, and AE onset time intervals 
 ○ <3 months ○ \geq3 and <6 months ○ \geq6 and <9 months ○ \geq9 and <12 months ○ \geq12 months • SOC, PT, and average number of migraine attacks treated with study treatment per month 
 ○ \geq2 ○ \geq4 ○ \geq6 	From randomization date to Visit 16 for participants with Visit 16, or within 30 days after last visit or last treatment, whichever is later, for participants without Visit 16	Categorical descriptives

Parameter	Description	Timing	Methodology
	
 ○ ≥8 • SOC, PT, and severity • SOC, PT, and causal relationship to the study treatment • Type (Mild, Moderate, Severe, related, not related) • SOC and PT for TEAEs occurring in ≥ 2% of participants in any ubrogapant treated dose group (and greater than placebo) 		
Common TEAEs	Summary by PT 
 • Includes TEAEs occurring in ≥ 2% of participants in any treatment group 	From randomization date to Visit 16 for participants with Visit 16, or within 30 days after last visit or last treatment, whichever is later, for participants without Visit 16	Categorical descriptives
On-therapy SAEs ¹	Overall summary and by PT	From randomization date to Visit 16 for participants with Visit 16, or within 30 days after last visit or last treatment, whichever is later, for participants without Visit 16	Categorical descriptives
On-therapy fatal SAEs	Participants who report On-therapy fatal SAEs will have their fatal SAEs and all AEs listed	From randomization date to Visit 16 for participants with Visit 16, or within 30 days after last visit or last treatment, whichever is later, for participants without Visit 16	Categorical descriptives
AEs leading to discontinuation ²	Overall summary and by PT	From randomization date to Visit 16 for participants with Visit 16, or within 30 days after last visit or last treatment, whichever is later, for participants without Visit 16 ²	Categorical descriptives

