TEAEs of specific interest ³	Overall summary and by PT for the following type of TEAEs: 
 • Hepatic Injury TEAEs • Cardiac Arrhythmias TEAEs • Central Nervous System Vascular Disorders TEAEs • Embolic and Thrombotic Events TEAEs • Hypertension TEAEs • Ischaemic Heart Disease TEAEs • Suicide/self-injury TEAEs • Triptan-associated TEAEs • Abuse-related TEAEs 	From randomization date to Visit 16 for participants with Visit 16, or within 30 days after last visit or last treatment, whichever is later, for participants without Visit 16	Categorical descriptives

SOCs will be sorted alphabetically; PTs will be sorted in descending frequency in the highest dose group.

If more than 1 AE is coded to the same participant, the participant will be counted only once for that preferred term using the greatest severity

Parameter	Description	Timing	Methodology
-----------	-------------	--------	-------------

If more than 1 AE is coded to the same participant, the participant will be counted only once for that preferred term using the strictest causal relationship to treatment for the summarization by causal relationship

¹ Participants who report ≥ 1 SAE will have their SAE listed.

² If the discontinued date is from randomization date to Visit 16 for participants with Visit 16, or within 30 days after last visit or last treatment, whichever is later, for participants without Visit 16, then AEs leading to discontinuation will be summarized and listed

³ Participants who reported ≥ 1 AEs in the corresponding category will have these AEs listed.

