5.2 Changes in the Conduct of the Study or Planned Analyses

Prior to database lock, there were no changes in study conduct or planned analyses from what was described in the protocol and detailed in the SAP.

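### The protocol plans one adverse-event summary as a count of events; the SAP's matching row, as written, counts participants, and no change is declared

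*Protocol*

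**What the plan says.** Protocol 7.3.2.1 plans two kinds of TEAE summary. The first is the number and percentage of patients by system organ class and preferred term, split further by severity and causality. For that table, "the patient will be counted only once for that preferred term using the greatest severity and strictest causality". The second has its own paragraph and a different unit: "The total number of TEAEs by severity and causal relationship to the study treatment will be summarized by treatment group".

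SAP 5.1.1.4.2 introduces Table 5-20, which holds all the adverse-event summaries, with one rule: "Unique participants reporting AEs in the following AE categories will be summarized by treatment group for the Safety Population as follows". Within the TEAE row, severity and causality by preferred term have their own bullets. A separate bullet begins "Type (Mild, Moderate, Severe, related, not related" and names no system organ class or preferred term. The method for the whole row is Categorical descriptives. SAP Table 5-2 defines this as "Number and percentage of participants in individual categories", with the rule "Participants with ≥ 1 qualifying event counted once per individual category". A footnote to Table 5-20 adds that "the participant will be counted only once for that preferred term using the greatest severity".

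SAP 5.2 states that before database lock "there were no changes in study conduct or planned analyses from what was described in the protocol".

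**The concern.** The Type bullet covers the same severity and causality categories as the protocol's event total, and no other Table 5-20 row could be that total. The SAP therefore seems to keep the table but lose its unit. A programmer working from the SAP text would produce participant counts, and a reader comparing the report with the protocol would find a planned summary missing with no explanation.

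The unit matters here because the drug is taken repeatedly. The objective is tolerability of intermittent treatment over a year, and the SAP tabulates exposure by attacks and doses. An event total is the only summary in the protocol's adverse-event section that rises when the same patient has the same event again. Without it, the planned adverse-event tables say how many patients were affected but not how many events there were.

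**Working it through.** The plan gives no figure to reproduce. The check is a comparison of text, followed by arithmetic to show what the unit changes.

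**1. Does the protocol's sentence mean events?** The preceding table is stated in patients and is already split by severity and causality. If the later sentence also meant patients, it would largely repeat that split. Its stated unit is the number of TEAEs. It is an event count.

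**2. What unit does the SAP give the matching row?**
- Lead-in to Table 5-20: unique participants.
- Method for the TEAE row: number and percentage of participants, each counted once per category.
- Wording of the Type bullet: no mention of events.

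All three point to participants. By contrast, the row for adjudicated ALT or AST elevations in SAP Table 5-21 uses the same method label but explicitly asks for incidence by participants and by events. When the SAP wants events, it can say so.

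**3. Is the change declared?** Not in SAP 5.2, nor in the legible list of amendments in SAP Section 7. The SAP cites protocol Amendment 2 and the current protocol is Amendment 3, but the legible Amendment 3 entries for 7.3.2.1 do not touch the event-total sentence. The version gap does not explain the difference.

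**4. How many episodes could one participant have?** Protocol Table 2 allows up to 8 treated attacks and 16 doses per 4 weeks; the study lasts 52 weeks.
- 52 / 4 = 13 four-week periods
- 13 × 8 = 104 attacks
- 13 × 16 = 208 doses

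These are ceilings, not expected use.

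**5. Illustration.** Arm size is 400 (protocol Section 3). The proportion affected, p, is an assumption, taken from 2% to 10%. Assume each affected participant has one recurring event, always of the same severity and causality, and that no one else falls in that cell. The formula is events = 400 × p × episodes each. The middle column takes 2 attacks a month × 12 = 24 episodes; 2 a month is the minimum average use in the interim-analysis trigger (SAP 5.1.1.6).

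| p | Type cell under the SAP | 1 episode | 24 episodes | 104 episodes |
|---|---|---|---|---|
| 2% | 8 (2.0%) | 8 | 192 | 832 |
| 5% | 20 (5.0%) | 20 | 480 | 2080 |
| 10% | 40 (10.0%) | 40 | 960 | 4160 |

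The participant count is constant along each row; the event count is not.

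**6. Sensitivity to recording.** Protocol 9.1.1 asks about events since the last visit, and SAP Table 6-6 has 13 scheduled visits from Week 4 to Week 52. If a site made one record per visit interval however often the event recurred, each participant could contribute at most 13 records. At p = 5% that is 20 × 13 = 260, and across the range 8 × 13 = 104 to 40 × 13 = 520. The event count still exceeds the participant count, but by much less than the ceilings suggest.

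**The case against.** **The unit of the Type bullet is inferred.** It comes from a general lead-in and a method label, and the label is used loosely: it also covers the Table 5-21 row that reports events and a Table 5-20 row that is really a listing. The bullet's position, apart from the preferred-term bullets, fits an intended event total. That may well have been the intention. But Table 5-21 states events and this row does not, so the text still needs changing.

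**Part of the plan is out of view.** Table shells are in a separate document and parts of the SAP are redacted or removed. A shell may already show events. If so, it would contradict the SAP text, and the same correction would be needed.

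**A reader might infer that the SAP turned every adverse-event table into participant counts.** It did not. The protocol itself counts patients in its system organ class and preferred term, serious-event, discontinuation and clinical-interest tables. There the two documents agree.

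**A reader might infer that recurrence is invisible.** It is not wholly so. The table by onset interval can count a recurring event once in each of five intervals. TEAEs are also tabulated by average attacks treated per month, and listings keep the individual events. Nor would the protocol's total show which term recurs, because it is not broken down by preferred term.

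**A reader might infer a masked signal against usual care, or a loss of power.** The documents support neither. They give no adverse-event rates, and the safety tables are descriptive with no test planned.

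**Conclusion.** The point holds for one summary. The protocol plans a total number of TEAEs by severity and causality; the SAP row that corresponds to it is, as written, a participant count; and the visible SAP declares no change. This is wrong as written and small to correct.

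Its effect is that total event burden is missing from the planned adverse-event tables for a drug that may be used for up to 104 attacks in a year. The gap between the two counts cannot be estimated from the documents. At an assumed 5% affected, it ranges from none (20 against 20) to 20 against 2080 at the permitted ceiling, or 20 against 260 if repeats are recorded once per visit interval. These figures show only what the unit does. They do not forecast the results.

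The conclusion rests on reading Type as the counterpart of the protocol's event total, and on the SAP text governing where the table shells cannot be seen.

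**What to change.** In SAP Table 5-20, define the Type row as the number of TEAEs (events) by severity and by causal relationship, per treatment group, within the row's existing window from randomization. State that for this row the unique-participant lead-in, the counted-once method and the greatest-severity and strictest-causality footnotes do not apply: each event is counted at its own severity and causality. Check that the table shell agrees. If the sponsor did mean to replace the event total with participants, SAP 5.2 should declare it.

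Optionally, because the total does not show which term recurs, print the number of events beside n (%) in the common-TEAE table. For the ubrogepant arms, events per 100 treated attacks could be added, using the attack counts already derived in SAP 5.1.1.4.1. Neither document plans these additions, and the correction does not depend on them.

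The cost is a change of SAP wording and at most a few extra columns; the adverse-event and dosing records already exist. The downside is that event counts depend on sites entering repeat episodes as separate records, and that open-label reporting may differ between usual care and ubrogepant. Footnote both.
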